### 8.3.3 CLASSIFICATION OF AN ADVERSE EVENT

#### 8.3.3.1 SEVERITY OF EVENT

The following guidelines will be used to describe severity.

- **Mild** – Events require minimal or no treatment and do not interfere with the participant's daily activities.
- **Moderate** – Events result in a low level of inconvenience or concern with the therapeutic measures. Moderate events may cause some interference with functioning.
- **Severe** – Events interrupt a participant's usual daily activity and may require systemic drug therapy or other treatment. Severe events are usually potentially life-threatening or incapacitating. Of note, the term "severe" does not necessarily equate to "serious".

#### 8.3.3.2 RELATIONSHIP TO STUDY INTERVENTION

All adverse events (AEs) and Adverse Device Effects (ADEs) must have their relationship to study intervention assessed by the clinician who examines and evaluates the participant based on temporal relationship and his/her clinical judgment. The degree of certainty about causality for adverse events will be graded using the categories below.

- **Definitely Related** – There is clear evidence to suggest a causal relationship, and other possible contributing factors can be ruled out. The clinical event, including an abnormal laboratory test result, occurs in a plausible time relationship to study intervention administration and cannot be explained by concurrent disease or other drugs or chemicals. The response to withdrawal of the study intervention (de-challenge) should be clinically plausible. The event must be pharmacologically or phenomenologically definitive, with use of a satisfactory re-challenge procedure if necessary.
- **Probably Related** – There is evidence to suggest a causal relationship, and the influence of other factors is unlikely. The clinical event, including an abnormal laboratory test result, occurs within a reasonable time after administration of the study intervention, is unlikely to be attributed to concurrent disease or other drugs or chemicals, and follows a clinically reasonable response on withdrawal (de-challenge). Re-challenge information is not required to fulfill this definition.
- **Potentially Related** – There is some evidence to suggest a causal relationship (e.g., the event occurred within a reasonable time after administration of the trial medication). However, other factors may have contributed to the event (e.g., the participant's clinical condition, other

concomitant events). Although an AE may rate only as “possibly related” soon after discovery, it can be flagged as requiring more information and later be upgraded to “probably related” or “definitely related”, as appropriate.

- **Unlikely to be related** – A clinical event, including an abnormal laboratory test result, whose temporal relationship to study intervention administration makes a causal relationship improbable (e.g., the event did not occur within a reasonable time after administration of the study intervention) and in which other drugs or chemicals or underlying disease provides plausible explanations (e.g., the participant’s clinical condition, other concomitant treatments).
- **Not Related** – The AE is completely independent of study intervention administration, and/or evidence exists that the event is definitely related to another etiology. There must be an alternative, definitive etiology documented by the clinician. As noted in 8.3.2, because of the nature of the disease population being studied, and the fact that that part of the study includes studying subjects experiencing a COPD exacerbation which may require hospitalization, hospitalization will NOT obligatorily be considered an SAE for this study. Hospitalization will be reported as an SAE if, in the discretion of the investigator, it is temporally related to albuterol use.

#### 8.3.3.3 EXPECTEDNESS

The principal investigator or co-investigators will be responsible for determining whether an adverse event (AE) is expected or unexpected. An AE will be considered unexpected if the nature, severity, or frequency of the event is not consistent with the risk information previously described for the study intervention.

#### 8.3.4 TIME PERIOD AND FREQUENCY FOR EVENT ASSESSMENT AND FOLLOW-UP

The occurrence of an adverse event (AE) or serious adverse event (SAE) may come to the attention of study personnel during study visits and interviews of a study participant presenting for medical care, or upon review by a study monitor.

All ADEs, SAEs, and AEs including local and systemic reactions not meeting the criteria for SAEs will be captured on the appropriate CRF. Information to be collected includes event description, time of onset, clinician’s assessment of severity, relationship to study product (assessed only by those with the training and authority to make a diagnosis), and time of resolution/stabilization of the event. All AEs occurring while on study must be documented appropriately regardless of relationship. All AEs will be followed to adequate resolution.

Any medical condition that is present at the time that the participant is screened will be considered as baseline and not reported as an AE. However, if the study participant’s condition deteriorates at any time during the study, it will be recorded as an AE.

Changes in the severity of an AE will be documented to allow an assessment of the duration of the event at each level of severity to be performed. AEs characterized as intermittent require documentation of onset and duration of each episode.

The study coordinator will record all reportable events with start dates occurring any time after informed consent is obtained until 24 hours after the last day of study participation. Events will be followed for outcome information until resolution or stabilization. Given the duration of the study, these events will be collected during the monthly phone calls by the study coordinator, unless the information is voluntarily provided by the subject in between study visits or phone calls.

---

### 8.3.5 ADVERSE EVENT REPORTING

In keeping with good clinical practice or good pharmacovigilance practice, and 21 C.F.R. Part 314 as the case may be, the external investigator will be required to report and notify the Teva Pharmaceuticals (Teva) of all situations mentioned below, within twenty-four (24) hours from receiving information of the situation. The event will be reported to Teva by submitting the collected information to the Teva Local Safety Officer. The event will also be reported to the FDA, Institutional Review Boards (IRBs), and any other collaborators/investigators according to national, and local safety reporting requirements.

- (a) All related Serious Adverse Events
- (b) All Serious Adverse Device Effects
- (c) Any exposure of a pregnant study participant to the study drug within thirty (30) days of exposure
- (d) Any medical event which may reasonably be believed to impair the integrity, validity or ongoing viability of the study

Each adverse event is to be classified by the investigator as serious or non-serious. This classification determines the reporting procedures to be followed. If a serious adverse event occurs, expedited reporting will follow FDA and IRB regulations. If an adverse event is both serious and unexpected, reporting will follow IRB reporting regulations as appropriate. SAEs are reportable from the time that the subject provides informed consent, which is obtained prior to the subject's participation in the trial (i.e., prior to undergoing any trial-related procedure through and including 24 hours after the final call). Any serious adverse event occurring at any other time during the study must be promptly reported if a causal relationship to study drug is suspected.

If a serious adverse event occurs, the Institutional IRB will be notified within five business days of awareness of the event by the investigator. The study coordinator may initiate the IRB notification, but it must be filed by the study investigator or co-investigators. If the serious adverse event is fatal or life threatening, notification to the Institutional IRB must be made within 24 hours, irrespective of the extent of available adverse event information. This timeframe also applies to additional new information (follow-up) on previously forwarded serious adverse event reports.

The MedWatch 3500A form should be utilized to report serious adverse events to the FDA.

All adverse events (serious and non-serious) will be reported on the adverse event page(s) of the CRF. Adverse events should be reported using concise medical terminology on the CRFs. Non-serious AE's will be reported annually to the IRB as appropriate.

---

### 8.3.6 REPORTING EVENTS TO PARTICIPANTS

Not applicable.

---

### 8.3.7 ADVERSE EVENTS OF SPECIAL INTEREST

Not applicable.

## 9 STATISTICAL CONSIDERATIONS

### 9.1 HYPOTHESIS

We hypothesize that inhaler metrics (PIF, inhalation volume, rescue inhaler use) will vary among COPD populations. We also hypothesize that increased albuterol use will positively correlate with worse daily Leikert scores, declining PIF, lower inhalation volume and higher CAT scores. We hypothesize that self-reported albuterol use will be lower than actual albuterol use captured by the DAQ app. We hypothesize that increased albuterol use will positively correlate with more symptomatic DAQ responses. The proposed study is designed to yield an initial exploration of the metrics captures by the Digihaler in a COPD population.

### 9.2 SAMPLE SIZE RATIONALE

The primary considerations in choosing the proposed target sample size were patient availability, fiscal costs, time required to complete the study, the proportion of subjects expected to complete the protocol, and conjectures about the precision of the estimators of interest. As such, this pilot study does not have pre-specified power calculations. Although this study will not be powered to make meaningful assessments of inhaler metric changes at the time of an AECOPD, we are permitting patients recently discharged for an AECOPD event to be enrolled, which will permit assessment of changes during the recovery phase as well as enrich for individuals more likely to have an AECOPD event during study.

### 9.3 MISSING DATA

The primary analyses will be “per protocol” analyses. Adult subjects must complete baseline and one month phone visit at minimum to be included in analysis. Subjects who complete these required visits will be included for analysis, and subjects who do not complete required visits will be excluded from the statistical analyses. Safety analyses will be included for all subjects. Reasons for drop-out and missing data values will be documented in the database. The occurrences of drop-out and missing data will be examined to investigate potential induction of selection biases. Missing data (i.e., occurring during hospitalization) will be assumed to be missing not at random. These missing data will not be imputed.

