## 1.3 SCHEDULE OF ACTIVITIES (SOA)

Procedures	Screening & Enrollment Virtual Visit	Confirmatory Phone Call	Phone visit #1	Phone visit #2	Phone visit #3
Time Window (days)	-21	0	30 $\pm$ 7	60 $\pm$ 7	90 $\pm$ 21
Informed consent	X				
Demographics	X				
Medical history	X				
Confirmation of Device Set-Up		X			
COPD Assessment Test	X		X	X	X
COPD Exacerbation History	X		X	X	X
Inhaler Use and Compliance	X		X	X	X
Adverse Event Assessment		X	X	X	X
Complete Case Report Forms (CRFs)	X	X	X	X	X

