#### **Specific Data Collection Includes:**

Clinical Data: Enrollment characteristics including age, race, sex, smoking history, prior spirometric data (FEV1, FEV1% predicted, FVC, FVC % predicted, FEV1/FVC), exacerbation history, enrollment inhaler regimen, self-reported frequency of albuterol use, baseline CAT score

Data Collection Tools: Enrollment questionnaire, CAT questionnaire, monthly AECOPD and self-reported albuterol use questionnaire, and Digihaler device. The Digihaler uses integrated sensors to capture inhalation data and stores it onto an e-module inside the device. When within range, the e-module transfers the stored data using Bluetooth technology to a paired app on the users' phone. The app can display the data in various reports as well as export the reports in the form of pdfs which can be emailed. The app also shares the data to a server via a wifi connection which enables real-time data sharing to a provider facing dashboard. The data the provider sees is the same as what patients see and also have the ability to be exported into a .csv file for further analysis. For additional data points, beyond what the patient and provider currently see, our team has the ability to export more information in the form of data extracts from the back end cloud server. This can be setup to send at a predetermined interval for further analysis.

**Patient Reported Outcomes (PROs):** CAT questionnaire, self-reported monthly average albuterol use during study, daily self-assessment asking “How are you feeling?” with responses provided on a Likert scale on the DAQ app, and Dihaler metric algorithm-triggered symptom questions using the DAQ app.

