## 6.2 STUDY INTERVENTION COMPLIANCE

Compliance with study interventions will be ensured by the study team during monthly.

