### 7.3 LOST TO FOLLOW-UP

A participant will be considered lost to follow-up if he or she is not able to be contacted on phone visit and no-longer is transmitting data via the DAQ app.

The following actions must be taken if a participant cannot be contacted:

- The site will attempt to contact the participant and reschedule the missed phone contact within 1 week and counsel the participant on the importance of maintaining the assigned visit schedule and ascertain if the participant wishes to and/or should continue in the study.
- Before a participant is deemed lost to follow-up, the investigator or designee will make every effort to regain contact with the participant (where possible, three telephone calls). These contact attempts should be documented in the participant's study file.
- Should the participant continue to be unreachable, he or she will be considered to have withdrawn from the study with a primary reason of lost to follow-up.

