### 9.4 STATISTICAL ANALYSES

Below are the pre-specific outcome measures:

Primary Outcome Measure:

1. Variability in Peak Inspiratory Flow (PIF) Measured via Digihaler Device (Time Frame: Three months)
  - b. PIF is the maximal flow occurring during an inhalation effort, expressed in Liters/minute. Mean, standard deviation and coefficient of variation (calculated by dividing standard deviation of PIF by the mean of the PIF) of daily PIF measurement collected over three months will be calculated. PIF will be measured using the Digihaler device.

Secondary Outcome Measures:

1. Correlation of Self-Reported Inhaler Use with Actual Inhaler Use (Time Frame: 3 months)

- a. Correlation between self-reported inhaler use and actual inhaler use over three months will be calculated with Spearman rank-order correlation coefficient. Self-reported inhaler use will be determined with an investigator-developed single question categorizing average use over the last four weeks with five groups (not at all, once a week or less, two or three times a week, one or two times a day, three or more times a day). Actual inhaler use will be directly measured via Digihaler device and categorized into one of the five groups described above.
2. Variability in Inhalation Volume Measured via Digihaler (Time Frame: Three months)
  - a. Inhalation volume is the volume of air inspired during an inhalation effort, expressed in Liters. The mean, standard deviation and coefficient of variation (calculated by dividing standard deviation of inhalation volume by the mean of the inhalation volume) of daily inhalation volume measurements collected daily over three months will be calculated. Inhalation volume will be measured using the Digihaler device.

The primary analysis will be descriptive, with analytical plans as defined above for each primary and secondary outcome.

The primary analysis will be descriptive, with analytical plans as defined above for each primary and secondary outcome.

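### Section 9.3 makes the month-1 phone visit a condition for analysing PIF, inhalation volume and inhalation counts, which the Digihaler records and transmits without any call

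*Combined protocol and SAP*

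**What the plan says.** Section 9.3 labels the primary analyses per protocol and sets the entry condition: "Adult subjects must complete baseline and one month phone visit at minimum to be included in analysis". It then adds that "subjects who do not complete required visits will be excluded from the statistical analyses". All subjects stay in the safety analyses. Neither 9.3 nor 9.4 defines another non-safety set or makes an exception for outcomes that come only from the device. Section 9.3 also undertakes a check: "The occurrences of drop-out and missing data will be examined to investigate potential induction of selection biases".

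On the source of the data, Section 9.4 says of the primary outcome that "PIF will be measured using the Digihaler device", and names the same source for inhalation volume and actual inhaler use. Section 6.1.1 describes the path from sensor to paired app to server: "The app also shares the data to a server via a wifi connection which enables real-time data sharing to a provider facing dashboard".

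Section 7.3 defines a participant as lost to follow-up when he or she is "not able to be contacted on phone visit and no-longer is transmitting data via the DAQ app".

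**The concern.** The entry condition does not match the data it controls. The monthly calls collect the CAT, self-reported albuterol use and exacerbation events; they supply no PIF, volume or count values. A missed month-1 call therefore says nothing directly about whether a participant has usable primary-outcome data. Conversely, a participant who completes that call but never transmits meets the rule while contributing nothing to the primary outcome.

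The purpose of the study is foundational data on normal variation in these metrics, from 60 participants and without a power calculation. At stake are usable observations on the primary outcome and the possibility that those who miss a call differ from those who do not.

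**Working it through.** The plan gives no figure for the number excluded, so there is nothing to reproduce. The check is mainly a reading of the sections together.

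**Step 1: who is excluded.** The Schedule of Activities places the first phone visit at day 30 ± 7. Section 7.3 requires an attempt to reschedule a missed contact within one week and, where possible, three telephone calls. Anyone still without a completed month-1 visit falls under the exclusion.

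**Step 2: what happens to them under 7.2 and 7.3.**

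| Participant | Status | Replaced under 7.2? | Device data analysed under 9.3? |
|---|---|---|---|
| Misses call 1, reached at call 2 or 3 | On study | No | No |
| Stays unreachable, treated as withdrawn under the last bullet of 7.3 | Withdrawn | Yes | No |
| Withdraws after receiving the device and before call 1 | Withdrawn | Yes | No |

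The opening definition in 7.3 requires both loss of phone contact and loss of transmission, while its last bullet turns on being unreachable. A transmitting participant who never answers could be read either way. On both readings 9.3 drops the data.

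**Step 3: what one exclusion removes.** One participant is 1/60 = 1.7% of the planned sample and up to 90 days of follow-up. Follow-up days are not recording days: someone using albuterol once a week, which Section 5.1 admits, has about 90/7 ≈ 13. A participant reached at calls 2 and 3 also loses two CAT and two self-report records.

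**Step 4: precision (illustration).** Assume that m participants are excluded without replacement, that the between-patient SD is unchanged, and that the outcome is a per-patient summary averaged over patients (9.4 does not state this).

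- Increase in standard error = √(60/(60 − m)) − 1
- m = 3: √(60/57) − 1 = 2.6%
- m = 6: √(60/54) − 1 = 5.4%

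The values of m are assumed.

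**Step 5: selection.** The shift in a cohort mean equals the excluded fraction times the difference between retained and excluded participants. The documents give neither factor, so neither size nor sign can be derived.

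**Step 6: what short series would do if included.** For n independent days, the expected sample SD is a(n) times the true SD, with a(7) = 0.959 and a(60) = 0.996.

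- Understatement at 7 days: 1 − 0.959 ≈ 4%. At an assumed day-to-day correlation of 0.3, simulation gives a(7) = 0.899, about 10%.
- Relative standard error of the SD, √(1 − a²): about 28% at 7 days and 9% at 60.
- With one recording day the SD and CV are undefined.

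**The case against.** The strongest defence is that the rule will seldom apply. There is a visit window, a rescheduling attempt, up to three calls and a $50 payment per completed call; Section 5.4 expects few retention problems; and Section 7.2 replaces participants who are withdrawn or discontinued. This stands as an argument about frequency. It narrows the unreplaced loss mainly to people who miss call 1 but are reached later, and it gives no ground for assuming many exclusions. It does not change what the rule does to those it catches, and replacement restores the headcount without recovering data already recorded.

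A second defence is that the call has a real function. The Schedule of Activities lists "Inhaler Use and Compliance" at each phone visit, and Section 6.2, in a sentence that breaks off, says "Compliance with study interventions will be ensured by the study team during monthly". The call also records exacerbations in the preceding month, which matters for describing variation in stable patients, and a later call may not recover the missed month. This stands in part. It bears most on counts, because the Digihaler is only the main route of SABA therapy, not necessarily the sole one. But the primary outcome definition in 9.4 does not exclude exacerbation days, the DAQ can capture some exacerbation information (6.1.1), and a missed call does not invalidate the PIF or volume of a recorded inhalation.

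Third, 9.3 already promises to look for selection bias. It does, but it names no analysis that brings the excluded device data back.

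A reader might infer that the rule biases the PIF variability estimate in a known direction, or that including all device data must reduce bias. The documents support neither: they contain nothing on how non-responders' variability compares with that of others, and short series themselves pull a per-patient SD downwards.

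**Conclusion.** The concern holds as a mismatch between the inclusion rule and the outcomes it governs, and is worth considering rather than critical. That 9.3 excludes these participants from all non-safety analyses, and that the device outcomes need no call, follow from the text with high confidence. The per protocol label is attached to the primary analyses, but the exclusion sentence is unrestricted and no other non-safety set exists.

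The likely precision cost is modest: the 2.6% and 5.4% increases rest on assumed losses of 3 and 6 participants, none replaced. It would be wrong to read this as showing that everyone who misses the call goes unreplaced, or that the primary result is biased by a stated amount. Withdrawn participants are replaced, and the size and direction of selection remain unknown.

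**What to change.** Amend Section 9.3 so that inclusion is set by outcome:

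- **PIF, inhalation volume and inhalation counts:** analyse all enrolled participants with device data, whatever calls they completed, including data recorded before withdrawal. Prespecify a minimum number of recording days for a per-patient SD and CV; it must be at least two.
- **Self-reported use and CAT:** require call data only for these outcomes, using every month available.
- **Sensitivity analysis:** report the month-1 per-protocol set alongside, so that the effect of the rule can be seen.

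The cost is a minor protocol amendment, which the Statement of Compliance says needs IRB approval. No new data collection is needed, although the device data available still depend on pairing, a wifi connection and in-app consent to share (2.3.1, 6.1.1). The downsides are that some short, less precise series enter and slightly understate a per-patient SD, and that compliance and exacerbation information for the missed month may be absent for those participants, which matters most for counts.
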